Appendix 9 Investigator Oversight of Study Personnel

All sites

All investigators for this study are qualified and licensed oncologists who are responsible for patient care and execution of the study. The investigator may use the infrastructure and delegate study-related activities to personnel at their site or external vendors as necessary. The investigators will need to fulfill their responsibilities as per Good Clinical Practice, including oversight of all health care providers and vendors who perform study-related activities delegated to them by the investigator.

The description of the operational processes for the specific format of the study conduct applicable to the site (physical site or virtual site) is described in detail in the county-specific operational manual.

In order to allow flexibility to participate in the study there are two operational approaches that *can* be used for study conduct *as* outlined below.

Virtual sites in the United States (Science 37 Metasites)

In the United States, these investigators will be geographically dispersed throughout the country. Investigators will sign a U.S. Food and Drug Administration (FDA) Form 1572.

The Science 37 study team is composed of investigators, mobile health care professionals (mHCPs), clinical research coordinators (CRCs), and the clinical study lead (CSL) who provides project management for the study. In addition to the study team members described above, Science 37 will use service providers for the conduct of the study (e.g., investigational medicinal product [IMP] management by a preferred IMP depot service provider).

All study-team members will receive protocol-specific training from Science 37 and the Sponsor. At the beginning of the study, a study protocol start-up/kickoff meeting will be held via teleconference to prepare the study team for conducting the study and to ensure the team is familiar with the study documentation, administrative procedures, responsibilities, and other relevant study information. The study team will complete additional protocol-specific training, if the protocol changes during the study.

The Science 37 study team will hold regular internal meetings via teleconference to discuss Science 37 operations and study execution. Topics for these meetings may include study status, regulatory updates, adverse events, changes to the protocol or other procedures, and any study-related information that may affect the patient or workflows. The frequency of meetings will be adjusted as necessary. The CSL will be responsible for planning, scheduling, and leading these meetings and will be supervised by the investigators. Meeting minutes will be distributed to ensure all staff are aware of what was discussed and the decisions made during the meeting.

Investigator responsibilities for providing supervision in this remote decentralized study are the same as they are in a conventional study and are consistent with those outlined in 21 CFR 312 and ICH E6 (R2) guidance.

Investigators will ensure that the study is conducted according to the investigational plan and that all applicable regulations for protecting the rights, safety, and welfare of patients are followed. The Science 37 Platform enables ongoing communication between all members of the study team. Investigators will communicate directly with the CSL, mHCP, and CRCs via teleconference, email, phone, text, or any appropriate and convenient mode of communication throughout the study as necessary. In addition, investigators will have real-time access to study *source* data within the Science 37 Platform.

Investigators in this study will delegate certain study-related tasks to other members of the study team. When an investigator delegates study-related tasks, he or she is responsible for providing adequate supervision of those to whom tasks are delegated. The investigator will ensure that all study staff adhere to the study protocol (i.e., inclusion and exclusion criteria, safety assessments, safety monitoring, assessment of adverse events and reporting of serious adverse events, reporting of unanticipated problems, etc.). Investigators will oversee mHCP activities by monitoring study-visit data within the Science 37 Platform, as well as during live study telemedicine interactions.

Study data will be collected during protocol-defined visits and entered *manually* into the eCRF. Investigators will complete protocol assessments and document directly into the platform. The responsibility for transcribing selected data into the eCRF may also be delegated to the study's CRC. In instances where the data are not directly entered into the eCRF by an investigator, the information will be made available for review during routine core study team meetings and via routine study activities/status update reports to be provided as part of the ongoing oversight process:

- Quality assurance reporting will be provided for investigator review addressing data types focused on the study-specific primary objectives and the data required to answer those objectives.
- Data entry and documentation that require regulatory submissions will be reviewed and signed off by the investigator (protocol deviations, Investigator's Brochure submissions, protocol amendments, etc.).

Any issues related to study operations and study personnel will be discussed during regularly scheduled meetings or escalated ad hoc as necessary. Relevant meeting discussions and decisions will be documented in meeting minutes, circulated for reference, and filed in the Investigator Site File.

Appendix 9: Investigator Oversight of Study Personnel

Issues related to the IMP that take place during delivery between Roche and the IMP depot or during storage at the depot will be reported to Roche by the IMP depot and/or Science 37 upon identification, in line with Roche's reporting requirements directed in the IMP management manual. The IMP depot will keep records of the communication and will inform Science 37 in a timely manner. IMP issues taking place after study drugs are shipped to the patients' homes will be documented in the Science 37 Platform and reported to Roche as instructed in the study protocol and IMP management manual.

The study team will ensure that all communication and records associated with this study, including those that demonstrate appropriate and required oversight, will be saved and archived. All research records will be available for inspection by authorized representatives of federal regulatory agencies, the Sponsor, and/or the Institutional Review Board. Each investigator will ensure that the following records in the Investigator Site File are maintained by Science 37, and the investigator will have access to review these documents in real time:

- A list of qualified persons to whom the investigator has delegated significant research-related duties
- All records submitted to the Institutional Review Board with evidence of approval
- All records of the disposition of the IMP
- Current curriculum vitae of the investigator and study personnel
- Appropriate documentation regarding study-specific Science 37 Platform access distinguishing all persons and roles authorized to make entries or corrections on data collection forms
- Reports to document findings of study monitoring

Physical Sites (Investigator-Associated Institutions) *in all countries, including the United States*

Science 37 may not be involved. The investigator will use the hospital infrastructure to conduct the study.

When physical study sites are used:

• There will be no Science 37 coordinator; rather, the site coordinator will conduct activities delegated by the investigator.

The site coordinator will liaise with the mHCP vendor to coordinate visits to the patient's home and set up the telemedicine sessions with the investigator and the patient.

- The investigational medicinal product can be managed by the hospital's pharmacy or by another licensed pharmacy if necessary.
- Safety samples can be analyzed by a central or a local lab (investigator's site).

Alectinib—F. Hoffmann-La Roche Ltd 149/Protocol BO41929, Version 4

Appendix 9: Investigator Oversight of Study Personnel

- The investigator will make arrangements for imaging assessments to be completed as per-protocol at a facility, ideally one that is close to the patient's home or to the investigator's site.
- The patient will be visited by a licensed mHCP who has been delegated to perform the assessments as per protocol.
- The investigator will use the hospital medical records as the source documents, including completed patient-reported outcomes and informed consent forms. The mHCPs will share their notes with the investigator as detailed in the country-specific operations manual. Data will be reported in RAVE by the investigator *or investigator delegate* as in the traditional clinical trial model, and on-site monitoring will take place at the investigator's site.

#### STATISTICAL ANALYSIS PLAN VERSION HISTORY

This Statistical Analysis Plan (SAP) was developed based on Roche SAP model document Version 2, 26 October 2020.

SAP Version	Approval Date	Based on Protocol (Version, Approval Date)
1	see electronic date stamp on title page	Version 4, 24 November 2021

#### LIST OF ABBREVIATIONS AND DEFINITIONS OF TERMS

Abbreviation or Term	Description			
AE	adverse event			
ALK	anaplastic lymphoma kinase			
BICR	blinded independent center review			
BID	twice a day			
CI	confidence interval			
CNS	central nervous system			
CR	complete response			
COVID-19	corona virus disease 2019			
CUP	cancer of unknown primary (site)			
DNA	deoxyribonucleic acid			
DOR	duration of response			
ECOG	Eastern Cooperative Oncology Group			
EORTC	European Organisation for the Research and Treatment of Cancer			
EQ-5D-5L	EuroQol 5-Dimension, 5-Level			
FMI	Foundation Medicine Inc.			
F1HEME	FoundationOneHeme test on blood			
F1CDx	FoundationOne CDx test on tissue			
F1LCDx	FoundationOne Liquid CDx test on blood			
ICH	International Council on Harmonization			
IMC	Internal Monitoring Committee			
MedDRA	Medical Dictionary for Regulatory Activities			
NCI CTCAE v5.0	National Cancer Institute Common Terminology Criteria for Adverse Events Version 5.0			
NGS	next-generation sequencing			
ORR	objective response rate			
OS	overall survival			
PR	partial response			
PFS	progression-free survival			
PRO	patient-reported outcomes			
PK	pharmacokinetic			
QoL	quality of life			
GHS/QoL	Global health status			
QLQ-C30	Quality of Life Questionnaire			
QTcF	QT interval corrected through use of Fridericia's formula			
RANO	Response Assessment in Neuro-Oncology			

- RECIST v1.1 Response Evaluation Criteria in Solid Tumors, Version 1.1
  - SAE serious adverse events
  - SAP Statistical Analysis Plan
  - SMQs standardized MedDRA queries

# 1. INTRODUCTION

This study will evaluate the efficacy and safety of alectinib in patients with anaplastic lymphoma kinase (ALK)-positive locally advanced or metastatic solid tumors other than lung cancer. Specific objectives and corresponding endpoints for the study are outlined in Table 1.

#### 1.1 OBJECTIVES AND ENDPOINTS

#### Table 1 Objectives and Corresponding Endpoints

E	Efficacy Objectives and Endpoints patients with anaplastic lymphoma kinase (ALK) fusion Solid Tumors (excluding Enrolled Patients with CUP and CNS Primary Tumors)			
	Primary Objective		Corresponding Endpoint	
•	To demonstrate a clinically relevant response to alectinib treatment	•	Confirmed objective response rate (ORR), defined as the proportion of patients with a complete response (CR) or a partial response (PR) confirmed $\geq$ 28 days after initial response, as determined by the investigator according to Response Evaluation Criteria in Solid Tumors, Version 1.1 (RECIST v1.1)	
	Secondary Objectives		Corresponding Endpoints	
•	The same as the primary endpoint	•	According to the blinded independent center review (BICR)	
•	To evaluate the duration of response (DOR)	•	DOR, defined as the time from the first occurrence of a documented objective response to disease progression or death from any cause (whichever occurs first), as determined by both the investigator and by BICR according to RECIST v1.1	
•	To evaluate progression-free survival (PFS)	•	PFS, defined as the time from first dose of alectinib treatment to disease progression or death from any cause, as determined by both the investigator and BICR according to RECIST v1.1	
•	To evaluate overall survival (OS)	•	OS, defined as the time from first dose of study drug to death from any cause	
E	fficacy Objectives and Endpoin	ts pa	atients with other Disease Characteristics	
•	To evaluate central nervous system (CNS) response in patients with measurable CNS metastases at baseline	•	CNS ORR, defined as objective tumor response rate (a CR or a PR) of CNS lesions by BICR according to RECIST v1.1	

Table 1	Objectives and	Corresponding	Endpoints (	cont.)
				. /

•	To evaluate the CNS duration of response	•	CNS DOR, defined as the time from the first observation of CNS response until the first observation of CNS progression or death from any cause by BICR according to RECIST v1.1
•	To evaluate the efficacy of alectinib in ALK fusion-positive patients with primary CNS tumors according to Response Assessment in Neuro-Oncology (RANO) criteria	•	ORR, DOR, and PFS as determined by both the investigator and BICR OS

•	To evaluate health status utility scores	•	Change from baseline in EuroQol 5- Dimension Questionnaire (5-level version; EQ-5D-5L) index-based and Visual Analog Scale (VAS) scores during study treatment

#### Table 1 Objectives and Corresponding Endpoints (cont.)

#### 1.1.1 Expression of Objectives and Endpoints using the Estimand Framework

The primary study objective and corresponding endpoint, as well as the main secondary efficacy objective and the corresponding secondary efficacy endpoints, are expressed using the estimand framework in Table 2, in accordance with the International Conference on Harmonization E9 (R1) statistical principles for clinical trials (ICH 2020).

Primary Efficacy Objective			Estimand Definition
•	To demonstrate a clinically relevant response to alectinib treatment	• Pc (e: tui ba to (re	opulation : Patients with ALK fusion solid tumors xcluding enrolled patients with CUP and CNS primary mors) with measurable disease at baseline who have a seline tumor assessment per the investigator according RECIST v1.1 and receive at least one dose of alectinib esponse-evaluable population)
		• Va pa in inv	ariable : Confirmed ORR, defined as the proportion of tients with a CR or a PR $\ge$ 28 days after initial response patients with solid tumors, as determined by the vestigator according to RECIST v1.1
		• Tr Bl otl	eatment : Experimental: alectinib at the dose of 600 mg D until disease progression, death, or withdrawal for any her reasons
		• Int	ercurrent events:
		• St	art of additional or alternative therapy
		• Ea	arly discontinuation from study treatment r any reason or withdrawal from study
		• Ha reg ap	andling of intercurrent events: A treatment policy with gards to the intercurrent events listed above will be oplied for the primary analysis.
		• Sι	ummary measure : Confirmed ORR
Main Secondary Efficacy Objective			Estimand Definition
•	To demonstrate a clinically relevant response to alectinib treatment	● Ac	cording to the blinded independent center review (BICR)

#### Table 2 Objectives and Estimands

ALK= anaplastic lymphoma kinase; BID=twice a day; CR=complete response; CNS=central nervous system; CUP=cancer of unknown primary (site); ORR=objective response rate; PR=partial response; RECIST= Response Evaluation Criteria in Solid Tumors.

## 1.2 STUDY DESIGN

This Phase II, open-label, single-arm study is designed to investigate the efficacy and safety of alectinib in patients with locally advanced or metastatic solid tumors (excluding lung cancer) that are determined to be ALK-positive per the Foundation Medicine Inc. (FMI) next-generation sequencing (NGS) test on tissue or blood (FoundationOne CDx [F1CDx] or FoundationOne Liquid CDx [F1LCDx] or FoundationOneHeme [F1HEME]).

ALK positivity determined per local accredited laboratory NGS-validated testing on tissue or blood may be accepted.

Patients can be identified by means of one of the two following enrollment pathways:

- 1. The Precision Enrollment approach offered by FMI. Briefly, when non-lung cancer samples are determined by FMI central testing to be positive for ALK, an FMI medical oncologist will contact the ordering physician (local oncologist) and provide information about the trial. If this is of interest to both the physician and the patient, enrollment procedures will begin.
- 2. Patients with ALK-positive NGS test results obtained outside FMI'S Precision Enrollment approach may be identified and the local ALK NGS test report will be made available (see Section 4.6.6) and will be assessed by the investigator for eligibility. The study team and Medical Monitor are to be consulted. If ALK positivity is not accepted per the criteria, prospective FMI testing is required and the patient may be enrolled if assessed to be ALK-positive by FMI.

Patients with both ALK-fusion and selected ALK mutations will be enrolled in the study. Enrollment will end once approximately 50 patients with ALK fusion solid tumors evaluable by Response Evaluation Criteria in Solid Tumors Version 1.1 (RECIST v1.1) have been recruited, regardless of the number of enrolled patients with primary central nervous system (CNS) tumors (evaluable according to Response Assessment in Neuro-Oncology [RANO] criteria), with cancer of unknown primary (site) (CUP) or ALK mutations.

The study schema is shown in Figure 1.

## Figure 1 Study Schema

ALK=anaplastic lymphoma kinase; BID=twice a day; ECOG=Eastern Cooperative Oncology Group; F/U=follow-up; RECIST v1.1=Response Evaluation Criteria in Solid Tumors, Version 1.1.

An interim, non-binding analysis will be performed once the first 15 RECIST v1.1 investigator-assessed response-evaluable patients with ALK fusions (excluding patients with primary CNS tumors and patients with CUP) have a response evaluation at 8 weeks available (unless they progressed or discontinued earlier from the study). If the analysis result shows that the response rate does not achieve at least 25% (4 responders), the study may be terminated due to futility.

The primary analysis will take place once all patients have been followed for a minimum of 24 weeks (i.e., three tumor assessments) to allow confirmation of any observed complete response (CR) or partial response (PR), unless they progressed or withdrew from sooner from the study.

The end of this study is defined as the date when the last patient, last visit, occurs or the date at which the last data point required for statistical analysis or safety follow-up is received from the last patient, whichever occurs later. The end of the study is expected to occur approximately in 2026.

In addition, the Sponsor may decide to terminate the study at any time.

The length of the study is expected to be approximately 5 years.

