Response will be assessed by the investigator on the basis of the CT and MRI scans according to RECIST v1.1 (see Appendix 5) or, for patients with primary CNS tumors, RANO criteria, which include neurological examination and corticosteroid use (see Appendix 6).

In addition, scans will be sent for BICR for assessment of responses according to RECIST v1.1 and, for patients with primary CNS tumors, according to RANO criteria.

Assessments performed by BICR will not be shared with the investigator and will have no impact on the management of the patient.

Tumor assessments performed as standard-of-care prior to obtaining informed consent and within 28 days prior to the first dose may be considered as baseline assessment if they satisfy the protocol criteria.

Scheduled tumor assessments should be kept according to the original scheduled based on the date of first dose administration, regardless of clinical visits delays and drug interruptions. At the investigator's discretion, tumor assessment may be repeated at any time if progressive disease is suspected (for example, in case of symptomatic deterioration).

An objective response should be confirmed by repeat assessments at least 4 weeks after initial documentation. No additional assessment is planned for 4 weeks after the initial response, but every effort should be made to obtain confirmation of response, even if a patient who has initially responded is withdrawn from study treatment for any reasons other than progression or death.

Patients who discontinue study treatment for any reason other than progression of disease or death should continue to have regular disease assessments every 8 weeks per the schedule of assessments (see Appendix 1) until progression.

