6.4 EFFICACY ANALYSES

6.4.1 Primary Efficacy Endpoint

The primary efficacy endpoint is ORR as assessed by investigator per RECIST v1.1, defined as the proportion of patients with an objective response. An objective response is defined as a CR or a PR per RECIST v1.1. Confirmation of objective response is required (confirmed \geq 28 days apart in two separate tumor assessments). Patients not meeting this criterion (including patients without a post-baseline tumor assessment) will be considered as non-responders.

An estimate of the ORR and its 95% CI using the Clopper-Pearson method will be calculated.

The primary efficacy analysis population consists of all patients with ALK fusion–positive solid tumors (excluding patients with CUP and primary CNS tumors) with measurable disease at baseline who have a baseline tumor assessment per the investigator according to RECIST v1.1 and have received at least one dose of study treatment.

An interim analysis will be performed as described in Section 6.9.

The primary analysis will take place once all patients have been followed for a minimum of 24 weeks (i.e., three tumor assessments) to allow confirmation of any observed CR or PR, unless they progressed or withdrew from sooner from the study.

6.4.2 Secondary Efficacy Endpoints

The secondary efficacy endpoints are presented in Section 2.1.2.

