## 5.3 PRIMARY ENDPOINT ANALYSIS

## 5.3.1 Definition of Primary Endpoint

The primary efficacy endpoint is confirmed ORR as determined by the investigator in patients with ALK fusion solid tumors (excluding enrolled patients with CUP and CNS primary tumors). An objective response is defined as a CR or a PR according to RECIST v1.1. Confirmation of objective response is required (confirmed ≥ 28 days apart in two separate tumor assessments). Patients not meeting this criterion (including patients without a post-baseline tumor assessment) will be considered as non-responders. ORR is defined as the proportion of patients with measurable disease at baseline who have an objective response in the response-evaluable population.

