# 5.3.2 Main Analytical Approach for Primary Endpoint

An estimate of the confirmed ORR and its two-sided 95% CI using the Clopper-Pearson method will be calculated. The confirmed ORR will be tested against the minimal clinically relevant ORR of 30% in this tissue-agnostic, biomarker-defined population with no available treatment options at the 5% two-sided significance level, i.e., the lower limit of the Clopper-Pearson CI must be bigger than 30%.

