## 5.4 SECONDARY ENDPOINTS ANALYSES

## 5.4.1 Key Secondary Endpoint

The key secondary efficacy endpoint is confirmed ORR as determined by the BICR in patients with ALK fusion solid tumors (excluding enrolled patients with CUP and CNS primary tumors). The same analyses as for the primary endpoint will be applied.

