## 5.4.2 Supportive Secondary Endpoints

## 5.4.2.1 Duration of Response

DOR is defined as the time from the date of the first occurrence of a CR or a PR (whichever status is recorded first) to the date of the first documented disease progression or death due to any causes, whichever occurred first. The DOR will be assessed in patients who had a confirmed objective response during the study, as determined by the investigator or BICR per RECIST v1.1. Patients who have not progressed or died at the time of analysis will be censored at the last tumor assessment date. If no tumor assessments are performed after the date of the first occurrence of a CR or a PR, DOR will be censored at the date of the first occurrence of a CR or a PR. The Kaplan-Meier methodology will be used to estimate the median DOR and to construct survival curves. The Brookmeyer-Crowley methodology will be used to construct the 95% CI for the median DOR (Brookmeyer and Crowley 1982).

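### The 24-week minimum follow-up does not allow confirmation of every observed response: one first seen at week 24 in a patient at minimum follow-up is scored as a non-response

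*SAP*

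**What the plan says.** SAP 1.2 sets the primary analysis for when every patient is "followed for a minimum of 24 weeks (i.e., three tumor assessments) to allow confirmation of any observed complete response (CR) or partial response (PR"), except those who progressed or withdrew earlier. Protocol 6.4.1 and the synopsis give the same timing: "followed for a minimum of 24 weeks (i.e., three tumor assessments) to allow confirmation of any observed CR or PR".

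The other pieces are these:

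- **Scan schedule.** Protocol 4.6.5 and Appendix 1 schedule tumor assessments every 8 weeks, with a window of 5 days either side.
- **Confirmation.** SAP 5.3.1 requires two separate assessments at least 28 days apart. Otherwise: "Patients not meeting this criterion (including patients without a post-baseline tumor assessment) will be considered as non-responders".
- **Confirmatory scan.** Protocol 4.6.5 states: "No additional assessment is planned for 4 weeks after the initial response, but every effort should be made to obtain confirmation of response".
- **Success criterion.** SAP 5.3.2 requires that "the lower limit of the Clopper-Pearson CI must be bigger than 30"%.
- **BICR.** For BICR-confirmed ORR, the key secondary endpoint, SAP 5.4.1 states: "The same analyses as for the primary endpoint will be applied".

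Neither document says what happens to a response that is awaiting confirmation at the cut-off.

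**The concern.** The stated purpose of the 24 weeks is that any response seen can also be confirmed. The third of the three scans cannot do both jobs. It can confirm an earlier response, but a response that first appears on it has no later scan within the minimum follow-up. Such a patient may be a true responder and is counted as a failure.

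Two things are at stake. The primary test is a threshold on about 50 patients, so one reclassified patient can change the result. And because 24 weeks is only a minimum, the sponsor may wait for a pending confirmation or not. In an open-label trial with investigator-assessed response, that choice could be made knowing which responses are pending, so it should be fixed beforehand.

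**Working it through.** **1. The plan's own figure.** 24 weeks / 8 weeks = 3 assessments, at weeks 8, 16 and 24. This reproduces.

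**2. Which first responses can be confirmed by week 24?**

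| First seen | Earliest confirmation (+28 days) | Next scheduled scan | Confirmable by week 24 on schedule |
|---|---|---|---|
| Week 8 | Week 12 | Week 16 | Yes |
| Week 16 | Week 20 | Week 24 | Yes |
| Week 24 | Week 28 | Week 32 | No |

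The scan window does not change this. A week-16 scan 5 days late and a week-24 scan 5 days early are still 163 - 117 = 46 days apart, which is enough. A week-24 scan done 5 days early (day 163) cannot be confirmed before day 163 + 28 = 191, after day 168.

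**3. Does one patient matter?** Clopper-Pearson lower limits at N = 50: 23 responders give 31.81% (pass) and 22 give 29.99% (fail). At a true ORR of 46% the chance of exactly 23/50 is about 11%.

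**4. Size.** Inputs from the documents: N = 50, null 30%, target ORR 46%. Two inputs are assumptions:

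- *Share f of responses first seen at week 24*: 0 to 10%. The documents give no distribution.
- *Accrual r*: 1 to 4 patients per month, constant. The documents support only a floor. Five years (60 months, Protocol 3.2) less about 5.5 months for the last patient's 24 weeks leaves 54.5 months, and 50 / 54.5 = 0.92 per month.

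Patients exposed: m = r x 12/52 x w, where w is the number of weeks beyond 24 during which confirmation is still impossible. w = 8 if confirmation waits for the week-32 scan; w = 4 if a 4-week scan is obtained. Expected responders lost = m x 0.46 x f. Chance of at least one pending = 1 - (1 - 0.46f)^m. Exact power = P[Bin(50 - m, 0.46) + Bin(m, 0.46(1 - f)) >= 23], interpolated for non-integer m. With f = 0 nothing is lost and power is 55.48%.

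| w | r | m | Lost, f = 10% | P(at least one), f = 10% | Power, f = 10% |
|---|---|---|---|---|---|
| 8 | 1 | 1.85 | 0.085 | 8% | 54.53% |
| 8 | 2 | 3.69 | 0.170 | 16% | 53.57% |
| 8 | 4 | 7.38 | 0.340 | 29% | 51.64% |
| 4 | 4 | 3.69 | 0.170 | 16% | 53.57% |

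The largest loss is 55.48 - 51.64 = 3.84 points with w = 8, and 55.48 - 53.57 = 1.91 points with w = 4. The w = 4 row equals w = 8 at 2 per month because m is the same.

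**5. Dependence on N.** SAP 1.2 fixes N only loosely: "Enrollment will end once approximately 50 patients with ALK fusion solid tumors evaluable by" RECIST v1.1. Taking N = 48 to 52 as an illustration, the largest loss is 3.6 to 3.9 points, while base power itself ranges from 55.5% to 65.2%.

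**6. Direction.** At a true rate of 30% and N = 50, exact one-sided type I error is 1.23% with nothing lost and falls to 1.02% in the worst case above.

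The base of 55.5% is the exact power of the rule requiring at least 23/50. The plan's 70% is close to a normal approximation (68.0% to 69.5%). That is a separate matter and nothing here depends on it.

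**The case against.** The strongest reply is that this is loose wording and not a flaw. Scoring is already specified, since an unconfirmed response is a non-response. Any fixed cut-off leaves a first response on the last scan unconfirmed; at 32 weeks it would be the week-32 scan. The 24 weeks is a minimum whose stated purpose is confirmation, so waiting is consistent with the text. The size rests on a late-response share with no source, and zero is possible. The request for every effort at confirmation could bring a scan at week 28. The trigger also refers to all patients: if a CUP, primary CNS or mutation patient is dosed last, the last fusion patient already has more than 24 weeks.

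Most of this stands, and it limits the size. It does not make the sentence true. Even a prompt 4-week scan falls after week 24, and no passage requires the cut-off to wait.

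A reader might infer three stronger things that the documents do not support:

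- *That the analysis will be run at exactly 24 weeks.* It is a minimum; a later cut-off is allowed.
- *That the gap could produce a false positive or favors alectinib.* It only removes responders.
- *That slow accrual shows the effect to be negligible, or fast accrual shows it to be material.* The screening figure of more than 25,000 in Protocol 3.3.1 has no time unit, and the 5-year length gives only the floor above.

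**Conclusion.** The concern holds in a limited form. The plan claims a property that its schedule lacks: at minimum follow-up, a response first seen at week 24 cannot be confirmed and is scored as a non-response, by the investigator and by BICR alike. The effect is confined essentially to late first responses in the last-enrolled patients.

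Under the stated assumptions the cost ranges from nothing to 0.34 responders and 3.8 points of power at N = 50, and half that or less if 4-week scans are obtained. Permitted variation in N matters more. The bias is conservative. The reason to act is that one patient can decide the test, and that whether to wait should be settled before anyone knows which responses are pending. It should be changed, but it does not threaten the validity of the primary analysis.

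**What to change.** Keep the 24-week minimum and add to SAP 1.2:

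> If, when the last patient reaches 24 weeks, any response-evaluable patient has a first CR or PR, by investigator or by BICR, dated on or before that day and awaiting confirmation, the single data cut-off for all endpoints moves once, to the date of the next scheduled assessment of the last such patient. Responses first seen after the 24-week date do not trigger a further move. Responses unconfirmed at the final cut-off are non-responses.

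A single cut-off matters. If the later scan counted for ORR but not for DOR, the censoring rule in SAP 5.4.2.1 ("If no tumor assessments are performed after the date of the first occurrence of a CR or a PR, DOR will be censored" at the first-response date) would not fit, because a later scan would exist and have been used. With one cut-off for ORR, DOR, PFS and OS, that rule applies unchanged.

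A SAP-only change is enough for now, because SAP 5.1 gives the SAP precedence over the protocol for a regulatory filing. Protocol 6.4.1 and the synopsis can be aligned at the next amendment, which under Protocol 9.7 needs ethics and, where required, regulatory approval.

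Cost: no extra scans, since 8-weekly assessments already continue until progression. The primary analysis may be delayed by up to 8 weeks plus the 5-day window, plus BICR reading time, and only if a confirmation is pending. The move can only raise the confirmed response count, which is why it must be written down before the data are seen.
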